We will perform survival analysis (Cox proportional hazard model) to model the time to linkage to PrEP or ART by study arm with adjustment of covariates and confounders. We will also evaluate the performance of the ChemBio DPP HIV test and OraSure oral-fluid assay by calculating the sensitivity, specificity, positive predictive value (PPV), and negative predictive value (NPV).

d. Early stopping rules

NA

e. Secondary Analyses

- Performance accuracy of ChemBio DPP HIV test and OraSure compared to SOC algorithm for HIV
- Seroconversion sensitivity of ChemBio DPP HIV test and OraSure compared to SOC algorithm for HIV
- Performance accuracy of the DPP syphilis test vs lab-based treponemal test;
- Proportion HIV positive
- Performance accuracy of the POC VL test vs quant and qual Roche VL
- Agreement between HIV VL using plasma derived from remnant blood samples and HIV VL tested on plasma from separation cards compared
- Proportion with no syphilis history who needed treatment;
- Proportion in which the treponemal test had no added value
- Turn-around time of the POC test to determine if the patients would have been in the ED/STI clinic at the time the test result became available for the clinician (PrEP or ART provision)

f. Data Management Plan

Collection: JHU will be responsible for collecting all data for this program. JHU project staff will enroll participants into the study. Participants will complete computer-assisted self-interviews and the data will be stored in an electronic high-security password-

protected environment. Blood and oral fluid samples will be collected and submitted for laboratory analyses. Medical record information, including laboratory results, will be abstracted and linked to the individuals study record. All study data will be deidentified before submission to CDC.

Protection: To ensure that each respondent's information is protected, a unique study ID will be created for each participant and will be the only identifier included on the data collection instruments. Paper forms, when used, will be filed by the unique ID and date of interview and stored under lock and key; information collected on paper will be entered into the appropriate data system at the clinical study site and the paper forms will be destroyed within 5 years after the study has ended. In addition to the data policy, JHU will implement security procedures for any recipient systems, and information contained therein that cover all aspects of data handling for hard copy and electronic data, including:

- Ensuring project data are secured against improper disclosure or unauthorized use of information.
- Access to information only on a need-to-know basis, when necessary, in the performance of assigned duties.
- Notify the supervisor, the Project Director, and the CDC PO, within one (1) hour, if information has either been disclosed to an unauthorized individual, used in an improper manner, or altered in an improper manner.
- Report immediately to both the Project Director and the CDC PO all contacts and inquiries concerning information from unauthorized staff and non-research team personnel.

Data sharing: CDC will receive only deidentified data and specimens. Data will be stored at CDC in secure servers with access limited to CDC staff who will conduct analyses for publications and presentations. Specimens stored in the CDC Biorepository.

A Limited Data Set (LDS) will be shared with the CDC in accordance with the funding agreement. Before transmission to the CDC, the LDS will be approved by the JHM IRB.

Once the primary outcomes papers of the project have been published, data will be available from the CDC Project Officer or the JHU PI ([name]) by email. The requestor will provide a justification for the request and agree to include project staff from JHU and CDC on all publications or preventions.

Long-term preservation of public health data: Prior to the end of the of the cooperative agreement, JHU and CDC will determine a data disposition plan. The data disposition plan may include several actions including purging or destroying data, moving data to less expensive or more secure storage like the cloud or offline, copying files to legal hold archives, or encrypting sensitive content to protect against breaches.

9. Risks:

a. Medical risks, listing all procedures, their major and minor risks and expected frequency.

The major risks of participation in these studies are primarily related to HIV testing, but may also include risks specific to the research procedures. Participants may experience increased stress secondary to having discussions about HIV infection, risk factors for acquisition of HIV infection, discussion of past medical and sexual history and discussion of how to cope with a recent HIV diagnosis.

Participants may learn that they are HIV-infected as part of these studies. Participants with acute HIV infection may have additional stress because they may be symptomatic with HIV seroconversion. Blood draws can be uncomfortable and cause bruising.

Participants may perceive a loss of confidentiality by having records accessible to study staff, study monitors and JHU regulatory or fiscal oversight staff. Participants with a reactive point-of-care HIV test will speak with a DIS at the clinic to initiate partner services. Participants who test positive on laboratory tests after testing negative on all point-of-care tests will also receive DIS support.

b. Steps taken to minimize the risks.

Participant confidentiality will be paramount at all times. All conversations about sexual and other behaviors as well as medical history, and communicating laboratory results will take place in a private area. The procedures required for these research protocols are, for the most part, standard medical procedures that are carried out by highly qualified and experienced personnel.

Stress, anxiety, and depression (for subjects diagnosed with HIV infection as part of these studies) as a result of study participation will be minimized by periodic reassurance, careful explanation of study procedures and results, maintenance of an open, supporting attitude by all study personnel, and referral back to participants' primary providers for further evaluation and care as needed. Routine clinical tests will be performed in CAP-certified laboratories to ensure accuracy of the results. Immediate care for any medical complications due to the study procedures will be provided by the investigators within their areas of competence. Participants diagnosed with HIV as part of these studies will be referred for primary care. These studies will not provide HIV care or HIV treatment.

Study documents will be retained for a minimum of 2 years after study completion, and longer if required by the sponsor. Study records will be retained until a letter approving destruction of the records is received from sponsor; this letter will be kept with the regulatory file.

Each participating site will maintain appropriate records for this study, in compliance with ICH E6, Section 4.9, regulatory and institutional requirements for the protection of confidentiality of subjects. The site participating in this study will permit authorized representatives of the sponsor(s), and regulatory agencies to examine (and when required

by applicable law, copy) clinical records for the purposes of clinical site monitoring, quality assurance reviews, audits, and evaluation of study safety and progress.

c. Plan for reporting unanticipated problems or study deviations.

Study deviations occur when there is non-adherence to the Protocol and includes Informed Consent, enrollment, and other occurrences of non-adherence to the Protocol. Protocol deviations should be sent to the JHU IRB per the JHU IRB guidelines. Any protocol deviation that meets reporting requirements of the IRB will also be reported with the same timeliness to the Johns Hopkins IRB. All deviations from the Protocol must be addressed in the study subject source documents. The documentation should include the reason(s) for the deviation and all attempts to prevent or correct the deviation. The site must complete a Protocol Deviation Form documenting each protocol deviation. A completed copy of the Protocol Deviation Form must be maintained in the regulatory file as well as in the subject's source documents.

d. Legal risks such as the risks that would be associated with breach of confidentiality.

There are no anticipated legal risks to participants based on breach of confidentiality. Utmost care will be taken to ensure that participant data are protected and secure at all times. In addition, a Certificate of Confidentiality (CoCs) protects the privacy of research participants by prohibiting disclosure of identifiable, sensitive research information to anyone not connected to the research except when the subject consents or in a few other specific situations. National Institutes of Health (NIH) funded researchers whose institutions determine that their research involves collecting or using identifiable, sensitive information are automatically deemed to be issued a CoC through their award. Several Department of Health and Human Services (HHS) agencies (including the CDC) issue CoCs for research they fund.

Certificate of Confidentiality

Consistent with Section 301(d) of the Public Health Service Act, a Certificate of Confidentiality (CoC) applies to this research because this research is funded, conducted, or supported by CDC and the following is true:

- The activity constitutes biomedical, behavioral, clinical, or other research; and
- Individually identifiable (including coded) information or biospecimens will be obtained or used for research purposes or as defined at 45 CFR 46.102(e); and
- Biospecimens are collected as part of the research, and is there a small risk that some combination of the biospecimen and other available data sources could be used to deduce the identity of an individual; and
- The research involves information about an individual for which there is at least a very small risk, that some combination of the information, a request for the information, and other available data sources could be used to deduce the identity of an individual.

Therefore, CDC and any of its collaborators, contractors, grantees, investigators or collaborating institutions that receive “identifiable, sensitive information” as defined by subsection 301(d) of the Public Health Service Act shall not:

- Disclose or provide, in any Federal, State, or local civil, criminal, administrative, legislative, or other proceeding “identifiable, sensitive information” that was created or compiled for purposes of the research, unless such disclosure or use is made with the consent of the individual to whom the information, document, or biospecimen pertains; or
- Disclose “identifiable, sensitive information” or provide ISI to any other person not connected with the research.

Disclosure is permitted only when:

- Required by Federal, State, or local laws (e.g., as required by the Food, Drug and Cosmetic Act or required by state laws requiring the reporting of communicable diseases to State and local health departments), excluding instances of disclosure in any Federal, State, or local civil, criminal, administrative, legislative, or other proceeding;
- Made with the consent of the individual to whom the information, document, or biospecimen pertains; or
- Made for the purposes of other scientific research that is in compliance with applicable Federal regulations governing the protection of human subjects in research.

CDC and its collaborators and contractors conducting this research will establish and maintain effective internal controls (e.g., policies and procedures) that provide reasonable assurance that the research is managed in compliance with subsection 301(d) of the Public Health Service Act.

CDC will ensure: 1) that any investigator or institution not funded by CDC who receives a copy of identifiable, sensitive information protected by this Certificate, understands that it is also subject to the requirements of the Certificate; and 2) that any subrecipient that receives CDC funds to carry out part of this research involving a copy of identifiable, sensitive information protected by a Certificate understands that it is subject to subsection 301(d) of the PHS Act. Therefore, all study staff will receive training on the importance of protecting the confidentiality of human research subjects and of personal information acquired, including the collection of biological specimens.

All research subjects will be informed of the protections and the limits to protections provided by this Certificate through the informed consent process. All study staff who obtain consent from study subjects will be trained on how the Certificate protects the information collected and the limitations of the Certificate’s protections.

e. Financial risks to the participants.

There are no anticipated financial risks to the participants, there is no charge for any study-related expenditure.

10. Benefits:

a. Description of the probable benefits for the participant and for society.

The participants will probably benefit by having the opportunity for earlier diagnosis of HIV and syphilis infections, this will facilitate earlier treatment and avoidance of the sequelae of untreated STI. The participant will have the opportunity to learn more about their sexual health and will be referred for rapid start of treatment/prevention services as well as risk reduction counselling with a clinician.

Society may benefit through a) the reduction of spread of STIs in the community; b) participating in a study that may change CDC guidelines and improve HIV testing that will be available to all.

11. Payment and Remuneration:

a. Detail compensation for participants including possible total compensation, proposed bonus, and any proposed reductions or penalties for not completing the protocol.

There is no payment for participating in this study. However, participants will receive a reimbursement of \$40 for each in-person study visit attended and completed. Participants that complete in-person research clinic visits will also receive a parking voucher or two MTA bus tokens if applicable.

12. Costs:

a. Detail costs of study procedure(s) or drug (s) or substance(s) to participants and identify who will pay for them.

There is no charge for any study-related expenditure. All study procedures and test will be paid for by the study.

13. Transfer of Materials:

Transfer of biospecimens from Johns Hopkins to another organization for research purposes and receipt of biospecimens from an outside organization for your research must adhere to JHU policies for material transfer (<https://ventures.jhu.edu/faculty-inventors/forms-policies/>) and biospecimen transfer (https://hpo.johnshopkins.edu/enterprise/policies/176/39187/policy_39187.pdf?_af=0.622324232879).

Please complete this section if your research involves transfer or receipt of biospecimens.

a. Will you **receive** biospecimens from an external entity for this research?

No.

If “Yes”, please confirm you will secure an MTA/research agreement from the appropriate office (JHTV/ORA) prior to transfer.

b. Will you **transfer** biospecimens to an external entity as part of this research?

Yes. We will adhere to the Johns Hopkins “Transferring Human Biospecimens to Outside Organization” policy.

https://hpo.johnshopkins.edu/enterprise/policies/176/39187/policy_39187.pdf?_af=0.25523869118

(See: <https://ventures.jhu.edu/technology-transfer/material-transfer-agreements/>.)

If “Yes”, please address each of the following:

- 1) Describe the nature of the research collaboration with the external entity and the rationale for the transfer. (Include an explanation of your intellectual contribution to the design of the research study, resulting data and sharing, and participation in the planned publications.)

The Johns Hopkins team has designed the protocol in collaboration with the CDC. JHU will undertake data analysis in conjunction with the CDC. The JHU team will also take the lead on any future academic publications and collaborate with the CDC in these efforts. The CDC will store these samples in a biorepository, to allow cross validation with other samples from different populations and geographical regions.

The study team will transfer deidentified processed plasma separation cards to Roche Diagnostics for HIV testing as described in the exploratory aim (page 3). JHU will only share the study ID number assigned to each participant. Roche will share the testing results with the JHU team (HIV qual and quant). The JHU team will only share the aggregate level concordance of the results as compared to SOC testing performed at JHU.

- 2) Please confirm you will secure an MTA through the appropriate office (JHTV or ORA) prior to transfer.

Yes

- 3) If the biospecimens you intend to transfer were obtained through clinical or research procedures at Johns Hopkins and “Other” is selected in Item 4, Section 23, please submit the following items in that Section:

- a. A pdf version of a completed JHTV Online “Material Transfer Agreement Request Form for Outbound Material” <https://ventures.jhu.edu/technology-transfer/material-transfer-agreements/> OR a copy of the COEUS PD (Proposal Development Summary).

Submitted

- b. A completed Biospecimen Transfer Information Sheet https://www.hopkinsmedicine.org/institutional_review_board/forms/.

Submitted

A signed and dated “De-identified Human Subject Certification” https://livejohnshopkins-my.sharepoint.com/:w:/g/personal/[name]/ETANthXrGPVBmYs-UC59fUBu9b1An7tYUWh4GjiG2fH4Q?rttime=5kjTd-F410g

Submitted

- c. Approval documents from recipient site, if applicable.
d. Copies of the consent forms associated with the IRB protocols under which the biospecimens were collected, with language appropriate to this transfer highlighted.

Submitted

The name of the specialist you are working with in ORA to complete a contract/MTA.
[name].

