Secondary: A. To evaluate the performance of HIV POC serologic tests using fresh whole blood and oral fluid specimens at baseline in all participants against a reference lab HIV testing algorithm

B. To evaluate the seroconversion sensitivity of the HIV tests through serial follow-up and describe characteristics of persons in the process of seroconversion compared to those of persons with established infection.

Exploratory Aim: Evaluate the diagnostic and clinical performance of the Roche cobas® Plasma Separation Cards compared to point-of-care and nucleic acid tests in clinical settings. Remnant venous blood collected from a random subset of participants (up to N=100) may be spotted on Plasma Separation Cards, stored for a minimum of 4 hours and up to 56 days and then processed. Results will be compared against plasma HIV RNA levels to determine the sensitivity of POC NAATs at varying levels of viremia.

3. Background:

(briefly describe pre-clinical and clinical data, current experience with procedures, drug or device, and any other relevant information to justify the research)

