Treatment failure is not a component of this study.

Participants who provide consent and are enrolled, but who do not provide biological samples will be classified as early withdrawals.

Voluntary Withdrawal by a Participant: Participants may withdraw voluntarily from study participation at any time. Participants who withdraw will continue their care with the appropriate clinical service for evaluation and care.

h. Description of what happens to participants receiving therapy when study ends or if a participant's participation in the study ends prematurely.

NA. Treatment is not a component of this study.

i. If biological materials are involved, please describe all the experimental procedures and analyses in which they will be used.

Blood samples:

Blood:

- POC HIV and syphilis testing (DPP HIV-Syphilis System) – whole blood
- Plasma: POC HIV VL testing (Cepheid GeneXpert or comparable platform)
- Plasma: Reference laboratory-based HIV diagnostic (Roche Elecsys with reflex to Geenius and Roche cobas quantitative HIV-1 RNA tie-breaker) and HIV RNA testing (Roche cobas qualitative and quantitative test) as appropriate. Plasma remaining after HIV diagnostic testing will be retrieved by study staff and used for IRB-approved testing, and biorepository storage. All Roche cobas qualitative tests will be run retrospectively on frozen plasma with batched testing.
- Remnant blood collected from a random subset of participants (up to N=100) may be spotted on Plasma Separation Cards, stored and then processed. Results will be compared against SOC plasma HIV RNA viral load tests to determine the sensitivity of POC viral loads tests at varying levels of viremia.
- Serum: reference lab-based testing for treponemal antibody testing, and, if positive, RPR titer. Serum remaining after treponemal antibody testing will be retrieved by study staff and stored in the research laboratory for IRB-approved testing, and biorepository storage.

- For storage for testing with future HIV or syphilis assays

Oral fluid:

- OraQuick HIV antibody testing
- For storage for testing with future HIV assays (e.g., using the Chembio DPP sampletainer)

Randomization:

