For participants in the randomized group, all eligible consented participants will be randomized to receive one of two testing arms using a computerized randomization system in the ratio of 1:1. Participants will be randomized to receive either POC HIV VL plus SOC testing or SOC testing only. Randomization will be performed by research staff after informed consent and verification of all eligibility criteria have been performed.

Early Withdrawals:

Participants who have provided consent and are enrolled, but who do not complete all study procedures at the time of enrollment, will be removed from the study and classified as early withdrawals. Participants may also be removed from the study early for failing to follow instructions, if continuation is deemed potentially harmful, or for any other reason at the discretion of the study principal investigator.

6. Study sites:

The following study sites are planned for the conduct of this study.

1. Johns Hopkins Medicine Emergency Department (JHMED)
2. The John G. Bartlett Specialty Practice (JGBSP), Johns Hopkins Hospital
3. The Baltimore City Health Department (BCHD) Health and Wellness Center, Sexual Health Clinics

These sites have been selected to provide optimal settings for patient interaction, and to provide access to patients at high risk of HIV infection.

Potential participants may be seen at any of the sites mentioned below or the Clinical Research Units (CRU) at the Institute for Clinical and Translational Research (ICTR).

Johns Hopkins Hospital Emergency Department (JHHED) is located in East Baltimore, Maryland. (Drs. [name] and [name]). The mission of JHHED is to provide a patient-centered care experience by world-class emergency health care providers. The JHH ED serves a predominantly socioeconomically-disadvantaged population in the metropolitan area with 60% from Baltimore City, one of the localities hardest hit by the HIV epidemic and 33% from Baltimore County. JHH adult ED patient population is comprised of 15% previous or current injection drug users, with a high prevalence of sexually transmitted infections (STIs) [21-23] and 6% HIV seroprevalence[24]. In FY 2022, the JHH ED had approximately 60,000 adult patient visits. Of these, approximately 65% of the patients were Black or African American and 5% had previously-diagnosed HIV

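### The Plasma Separation Card subset is drawn at random without enrichment, so it is poorly matched to its aim of estimating sensitivity by level of viraemia

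*Combined protocol and SAP*

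**What the plan says.** The exploratory aim in Section 2 (Objectives) sets both the sampling rule and the purpose. The rule is that "Remnant venous blood collected from a random subset of participants (up to N=100) may be spotted on Plasma Separation Cards". The purpose follows: "Results will be compared against plasma HIV RNA levels to determine the sensitivity of POC NAATs at varying levels of viremia".

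Section 5i repeats the rule ("Remnant blood collected from a random subset of participants (up to N=100) may be spotted on Plasma Separation Cards, stored and then processed") and the purpose ("to determine the sensitivity of POC viral loads tests at varying levels of viremia").

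The only card analysis listed in Section 8e (Secondary Analyses) is "Agreement between HIV VL using plasma derived from remnant blood samples and HIV VL tested on plasma from separation cards".

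No section enriches or stratifies the subset by HIV status or viral load. None defines viraemia bands, sets a minimum number of viraemic specimens or a precision target, or says whether the cards come from the randomized group, the non-randomized group or both.

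**The concern.** Sensitivity at a given viral load can be estimated only from specimens with RNA at that level, and quantitative agreement only from pairs in which both methods return a value. A card from a person with no detectable RNA contributes to specificity and to neither of these. A random draw allocates cards in proportion to who is enrolled, so unless a large share of participants is viraemic, most of the 100 cards go to RNA-negative people. The few informative cards must then be divided among viral-load bands.

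At stake is whether the card evaluation can answer its own question. No primary, key secondary or safety conclusion depends on it.

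**Working it through.** The figure of 100 has no stated derivation, so there is nothing to reproduce. The check is how many informative cards it would yield, and with what precision.

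**Inputs from the protocol**
- Cards: up to 100 (Sections 2 and 5i).
- Johns Hopkins Hospital emergency department: "6% HIV seroprevalence", and "5% had previously-diagnosed HIV" infection (Section 6).
- Randomized group: 2 × 204 = 408. Non-randomized group: up to 1,100. Total: up to 1,508 (Section 8c).

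**Assumptions, because the protocol gives no figure**
- Viraemic share of people with HIV: 30-50%.
- Three equal viral-load bands.
- For the mixed-group calculation, 6-50% viraemic in the randomized group and 0-10% in the non-randomized group.

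**Step 1: emergency department figure applied to enrollees**
- HIV-positive cards: 100 × 0.06 = 6 (95% binomial range 2 to 11).
- Viraemic cards: 6 × 0.30 = 1.8, and 6 × 0.50 = 3.0.
- With X ~ Binomial(100, p), P(X ≥ 10) is 0.09% at p = 0.03. It is 7.8% at p = 0.06, that is, if everyone with HIV were viraemic.

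**Step 2: enriched enrolment**
- At 30% prevalence with half viraemic: 100 × 0.30 × 0.50 = 15.
- Cards drawn in proportion to planned enrolment: expected count = 100 × (408 × r + 1,100 × s) / 1,508, where r and s are the viraemic proportions in the randomized and non-randomized groups.
- Low end (r = 0.06, s = 0): 100 × 24.48 / 1,508 = 1.6.
- High end (r = 0.50, s = 0.10): 100 × 314 / 1,508 = 20.8.

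**Step 3: precision per band with perfect detection**

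When all n specimens are detected, the exact (Clopper-Pearson) 95% lower limit is 0.025^(1/n).

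| Viraemic cards | Per band | Lower limit |
|---|---|---|
| 3 | 1 | 2.5% |
| 6 | 2 | 16% |
| 15 | 5 | 48% |
| 20 | 6 | 54% |
| 30 | 10 | 69% |
| 50 | 16 | 79% |

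Without any banding, the lower limits are 29% for 3 of 3 and 54% for 6 of 6.

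**Step 4: the most that targeting could reach**
- People with HIV in the whole study at 6%: 1,508 × 0.06 ≈ 90.
- Viraemic among them: 90 × 0.30 ≈ 27, and 90 × 0.50 ≈ 45.
- If every one were captured, three bands would hold 9 to 15 each. The lower limits would be 0.025^(1/9) = 66% and 0.025^(1/15) = 78%.

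**The case against.** The strongest objection is that 6% describes general adult patients at one emergency department. Study enrolment is selected for high HIV and STI risk. The randomized group admits people with HIV only if they lack a documented undetectable viral load in the last six months or do not take medication daily (Section 5a). One site is a clinic caring for more than 3,000 people with HIV (Section 6). This stands. A reader might infer that the subset will certainly hold only a handful of viraemic people, and the documents do not support that. Step 2 gives about 2 to 21 under proportional sampling, and more if cards came mainly from the randomized group. In the other direction, the non-randomized group is the larger one and may include people on daily ART or PrEP.

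Second, the protocol says random without giving the sampling frame, so a simple random draw from everyone is one reading, not a stated fact. That is correct. It is a reason to state the frame.

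Third, the aim is exploratory, the cards are optional and 100 is a maximum. Section 13 says that only aggregate concordance with SOC results will be shared, and unselected cards do inform overall concordance and specificity. Section 8e also lists accuracy of the POC viral load test as a separate analysis that is not limited to these 100 people. All of this lowers the stakes. It does not align the sampling rule with the purpose stated in Sections 2 and 5i.

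Fourth, the aim evaluates the cards but names sensitivity of the POC nucleic acid test as its result. The SOC-only arm has no POC viral load, and the non-randomized group gets a Cepheid test only if resources permit (Section 5a). More viraemic cards would not supply that missing result. This stands, so the band-specific results that targeting can secure are those of the card itself.

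**Conclusion.** The point holds as a low-cost improvement to an exploratory aim. A random subset with no enrichment is a poor match for sensitivity by viraemia level and for viral-load agreement. About 2-3 informative cards are expected if 6% seroprevalence and a 30-50% viraemic share both apply to enrollees. About 15-20 are expected under more enriched assumptions, which leaves 5-6 per band and a lower limit of 48-54% even with perfect detection.

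A reader might go further and say that sensitivity cannot be estimated at all. That is too strong: an estimate would exist, and overall concordance would be informed. What is supported is that band-specific estimates would be too imprecise to be useful across this range. The viraemic shares and the three bands are assumptions, and a frame confined to the randomized group could do better. At 30% viraemic it would give about 10 per band, with a lower limit of 69%.

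**What to change.** 1. Keep the cap of 100 and replace the random rule with a priority order. First, take remnant blood from participants with detectable RNA on the study's plasma or POC viral load test, where that result is available while the blood can still be spotted. This route includes antibody-negative acute infection, which the rapid antibody tests would miss. Otherwise, take it from participants with a reactive rapid test or known HIV without documented suppression. This second route will also bring in some suppressed people.
2. Fill the remaining cards with a random sample of non-reactive participants, for specificity.
3. State the sampling frame and the viral-load bands, with expected counts and interval widths.
4. Report card sensitivity and agreement by reference viral-load band with exact intervals.
5. Do not promise 50 viraemic cards. At 6% prevalence the whole study would hold about 27-45 viraemic people (step 4).

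The cost is small. The number of cards does not rise, and rapid tests and HIV history are already collected at enrolment. Staff must check results before spotting, and the protocol does not say how much remnant blood is left for reactive participants once other testing and storage are served. The subset would no longer mirror the study population, so overall agreement must be reported by stratum or weighted by the sampling fractions.

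If targeting is not adopted, limit the aim to overall concordance and drop the objective concerning levels of viraemia from Sections 2 and 5i.
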